6. OBJECTIVES

PRIMARY OBJECTIVE

Fatigue-related quality of life of patients receiving a tyrosine kinase inhibitor evaluated using the validated 13-item FACIT-Fatigue scale for patients with metastatic renal cancer in Spanish.^{1,2}

SECONDARY OBJECTIVES

- 1) Quality of life in patients with palmar-plantar erythrodysaesthesia (hand-foot syndrome).
- 2) To assess the following adverse effects according to version 4 of the CTCAE (Common Terminology Criteria for Adverse Events): any grade of fatigue and HFS.
- 3) To study what role aerobic exercise (walking quickly, running, swimming, playing tennis, dancing and/or riding a bike) plays in the onset of fatigue before starting and during treatment.
- 4) To evaluate what impact the time of drug administration, napping, off-treatment periods, temporary treatment breaks and dose reductions have on controlling fatigue and hand-foot syndrome.
- 5) Time to Treatment Failure (TTF), defined as the time from the start of treatment with a tyrosine kinase inhibitor to tumour progression, treatment discontinuation for any reason or death from any cause.
- 6) Progression-Free Survival (PFS) (median): time from the start of treatment with a tyrosine kinase inhibitor to tumour progression or death from any cause.
- 7) Objective Response Rate according to RECIST version 1.1.

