ANNEX 8: FACIT-FATIGUE QUALITY OF LIFE QUESTIONNAIRE

Escala FACIT de fatiga (Versión 4)

A continuación encontrará una lista de afirmaciones que otras personas con su misma enfermedad consideran importantes. Marque un solo número por línea para indicar la respuesta que corresponde a los últimos 7 días.

		Nada	Un poco	Algo	Mucho	Muchí- simo
187	Me siento agotado(a)	0	1	2	3	4
HI 12	Siento debilidad en todo el cuerpo	0	1	2	3	4
Anl	Me siento decaido(a)	0	1	2	3	4
An2	Me siento cansado(a)	0	1	2	3	4
An3	Tengo dificultad para comenzar las cosas porque estoy cansado(a)	0	1	2	3	4
An4	Tengo dificultad para terminar las cosas porque estoy cansado(a)	0	1	2	3	4
An5	Tengo energía	0	1	2	3	4
An7	Soy capaz de hacer mis actividades habituales (trabajar, ir a la escuela, hacer las compras)	0	1	2	3	4
An8	Necesito dormir durante el día	0	1	2	3	4
An 12	Estoy demasiado cansado(a) para comer	0	1	2	3	4
An 14	Necesito ayuda para hacer mis actividades habituales	0	1	2	3	4
An 15	Estoy frustrado(a) porque estoy demasiado cansado(a) para hacer las cosas que quiero hacer	0	1	2	3	4
An 16	Tengo que limitar mis actividades sociales debido al cansancio	0	1	2	3	4

Spanish (Universal) Copyright 1987, 1997 17 December 2010 Page 1 of 1

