#### 7 HANDLING OF MISSING DATA

No criterion for replacing missing values will be used.

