## • Has taken the medication:

- In the morning (between 7 am and 12 noon)
- In the afternoon (between 1 pm and 7 pm)
- At night (between 8 pm and 6 am)
- I have not taken any medication this week

For each one of the weekly habits described above, a summary calculation will be made (after three months) of each patient's habits in terms of daytime rest, physical exercise and taking their medication, taking the options marked with greater frequency in the last 12 weeks into account.

FACIT\_Fatigue: The main measures of centrality and dispersion measures will be calculated (mean, standard deviation, median, minimum, maximum, IR and 95%CI ) from the score obtained in the FACIT\_Fatigue quality of life scale, calculated as described in ANNEX 1. The absolute and relative frequency of patients with severe fatigue, being those with a score of less than 30 points on the FACIT\_Fatigue scale, will also be presented.

For each one of the evolution visits (week 6, week 12, week 18, week 24, week 30 and week 36), a study will be performed to ascertain whether significant changes have occurred in fatigue-related quality of life versus the previous evaluation, and defined as:

- **Improvement:** if there is an increase of more than 4 points in the FACIT\_Fatigue scale score versus the previous evaluation
- **Maintenance:** if the score on the quality of life scale does not vary by more than 4 points versus the previous evaluation
- **Worsening:** if the score obtained on the Facit\_Fatigue scale decreases by more than four points versus the previous evaluation.

Significant associations will be sought between the habits of daytime rest, the practice of physical aerobic exercise, medication taken, dose and treatment schedule changes, dose interruptions and the number of days of treatment

interruption depending on the evolution in the evaluation of the fatigue in the FACIT\_Fatigue over the last six weeks. The Pearson chi-squared test will be used for this purpose (or Fisher's exact test for 2x2 tables or likelihood ratio test for mxn tables, if necessary).

- Treatment: For each one of the treatment cycles received by patients during the 9-month follow-up, the following will be studied:
  - **Dose change:** the absolute and relative frequency of patients who have changed doses since the last cycle will be provided. In the sub-population of patients with dose changes in the last cycle, their frequency distribution will be presented according to:

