#### Functional Assessment of Chronic Illness Therapy (FAC1T) Fatigue Scale (Version 4)

Below is a list of statements that other people with your illness have said are important. Please circle or mark one number per line to indicate your response as it applies to the past 7 days

		Not at all	A little bit	Somewhat	Quite a bit	Very much
1	I feel fatigued	0	1	2	3	4
2	I feel weak all over	0	1	2	3	4
3	I feel listless ("washed out")	0	1	2	3	4
4	I feel tired	0	1	2	3	4
5	I have trouble starting things because I am tired	0	1	2	3	4
6	I have trouble finishing things because I am tired	0	1	2	3	4
7	I have energy	0	1	2	3	4
8	I am able to do my usual activities	0	1	2	3	4
9	I need to sleep during the day	0	1	2	3	4
10	I am too tired to eat	0	1	2	3	4
11	I need help doing my usual activities	0	1	2	3	4
12	I am frustrated by being too tired to do the things I want to do	0	1	2	3	4
13	I have to limit my social activity because I am tired	0	1	2	3	4

Scoring: Items are scored as follows: 4=Not At all. 3=A Little bit; 2=Somewhat; l=Quite A Bit; 0=Very Much, EXCEPT items #7 and #8 which are reversed scored. Score range 0-52. A score of less than 30 indicates severe fatigue. The higher the score, the better the quality of life.

Item Number	Reverse Item?		Item Response	Item Score
1	4	-		=
2	4	-		=
3	4	-		=
4	4	-		=
5	4	-		=
6	4	-		=
7	0	+		=
8	0	+		=
9	4	-		=
10	4	-		=
11	4	-		=
12	4	-		=
13	4	-		=

Sum individual item scores: \_\_\_\_\_

Multiply by 13:

Divide by number of items answered:

For guidelines on handling missing data and scoring options, please refer to the Administration and Scoring Guidelines on-line at www.facit.org.

Source: Webster, K, Celia, D, & Yost, K. (2003). The functional assessment of chronic illness therapy (FACIT) measurement system: properties, applications and interpretation. *Health and Quality of Life Outcomes*, 1(79), 1-7.

Reprinted with permission from: http://www.facit.org/FACITOrg/Questionnaires

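### FACIT item 9 (need for daytime sleep) overlaps with the diary napping exposure in Table 3.4.1 and can inflate the association when napping changes between evaluations

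*SAP*

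**What the plan says.** Napping is a measure under evaluation. Secondary objective 4 in Protocol section 6 reads "To evaluate what impact the time of drug administration, napping, off-treatment periods, temporary treatment breaks and dose reductions have" on the control of fatigue and hand-foot syndrome. Protocol 7.1 and SAP 2.1 list napping among the measures to improve quality of life.

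- **Exposure.** The weekly diary has four napping categories, from every day to none (SAP 8.2.3). The only summary defined is the option marked most often over the last 12 weeks.
- **Outcome.** At weeks 6 to 36, each patient is classed as improved, maintained or worsened. A patient has worsened when the score on the "scale decreases by more than four points versus the previous evaluation". The SAP then states: "Significant associations will be sought between the habits of daytime rest, the practice of physical aerobic exercise", among other factors, and this classification. The association is tested by chi-square over the last six weeks (SAP 8.2.3; Table 3.4.1 in SAP section 9).
- **Score.** SAP Annex 1 states: "Score range 0-52. A score of less than 30 indicates severe fatigue". A higher score is better. Item 9 is "I need to sleep during the day", scored as 4 minus the response. The Spanish form in Protocol Annex 8 carries it as "Necesito dormir durante el día".

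The SAP plans no score without item 9, no sensitivity analysis and no caveat on the overlap. A separate table (3.2.1) sets daytime rest against CTCAE fatigue grade, which does not use the FACIT score.

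**The concern.** The exposure is how often a patient naps. Part of the outcome is how much the patient reports needing daytime sleep. A patient who takes up napping and answers item 9 accordingly loses FACIT points for that reason alone. Because this is shared content, measuring the exposure before the outcome would not remove it, and neither would adjusting for confounders.

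At stake is the FACIT part of objective 4. Napping could look unhelpful, or a benefit could be hidden, although the other 12 items show no difference.

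**Working it through.** **1. Weight of item 9.** 13 items × 4 points = 52, which reproduces the stated range. Item 9 is 4/52 = 7.7% of the score.

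**2. Can item 9 alone make a patient worsened?** With all 13 items answered its largest fall is 4 points, and worsening needs more than 4, so no. The exception is proration. Annex 1 multiplies the sum by 13 and then says "Divide by number of items answered". With 12 items answered, 4 × 13/12 = 4.33, which crosses the limit. SAP section 7 says "No criterion for replacing missing values will be used", so the two rules need reconciling.

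**3. One patient whose napping rises.** Assume that the six-week change in the other 12 items has mean 0 and SD 5. If item 9 costs s points, P(worsened) = Φ((−5 + s + 0.5)/5):

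- s = 0: Φ(−0.9) = 18%
- s = 1: Φ(−0.7) = 24%
- s = 2: Φ(−0.5) = 31%
- s = 3: Φ(−0.3) = 38%

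The SAP does not tabulate new nappers separately, so established nappers dilute these figures. If 25% of daily nappers are new and s = 2, then 0.75 × 18.4 + 0.25 × 30.9 = 21.5, about 22% against 18%. If 10% are new, 0.90 × 18.4 + 0.10 × 30.9 = 19.7, about 20%.

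**4. The planned test.** Simulation with n = 95 (100 less the SAP's 5% discontinuation), four napping levels by three change categories, Pearson chi-square at 0.05 and 3,000 runs per scenario (Monte Carlo standard error √(0.05 × 0.95/3000) = 0.4 percentage points at 5%). Napping affects item 9 only. These inputs are assumptions, because the documents give no figures:

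- Napping shares are 40% none and 20% in each other category.
- The item 9 response is 0, 1, 2 or 4 from none to every day, give or take 1.
- The SD of change in the other 12 items is 5, 7 or 9.
- The exposure is the habit at the later evaluation.

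Rejection rates with the 13-item score, and worsening at SD 7:

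| Habit between evaluations | SD 5 | SD 7 | SD 9 | Worsened, daily v none (SD 7) |
|---|---|---|---|---|
| Stable | 5.0% | 4.8% | 4.6% | 26% v 26% |
| Half redraw at random | 10.6% | 7.0% | 6.8% | 32% v 24% |
| All redraw at random | 32.2% | 17.0% | 11.8% | 38% v 21% |
| Nobody napped earlier | 31.2% | 16.4% | 12.3% | 45% v 26% |

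A redraw can return the same category, with probability 0.4² + 3 × 0.2² = 0.28. In the half-redraw row, therefore, 0.5 × 0.72 = 36% of patients actually change category.

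**5. Without item 9.** On the unscaled 12-item sum with the same limit, rejection is 4.3-5.5% in every scenario, and worsening is virtually equal in daily nappers and non-nappers.

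**6. Why not rescale to 13 items?** A raw fall of 4 becomes 4 × 13/12 = 4.33 and counts as worsening, where the 13-item total needs 5. At SD 5 with no overlap, worsening rises from Φ(−0.9) = 18% to Φ(−0.7) = 24%. The two columns would then differ for a reason unrelated to napping.

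**The case against.** The strongest reply is that the test sets a habit level against a change in score. With a stable habit, item 9 sits in both scores and cancels. The 12-week summary also dilutes a habit begun within the six-week FACIT window. Item 9 asks about felt need while the diary records naps taken, so the link is plausible but not definitional. Established nappers already at the floor of item 9 cannot fall further on it. Needing daytime sleep is a legitimate part of a validated scale, and this is one of several association tables in a study that calls itself descriptive.

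All of this stands as a limit on size. It rules out a reading that the title of Table 3.4.1 might invite, namely that napping and FACIT worsening are associated by construction. The first row of the simulation contradicts that. Nor do the documents show that the study would report the opposite of the truth about napping, since they give neither the share of patients who change habit nor how closely item 9 follows the diary.

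Stable habits are nevertheless not a safe default. The baseline questionnaire precedes treatment. The background in both documents places fatigue two to three weeks after the start and cites a phase I study linking asthenia with more daytime napping. SAP 8.2.3 itself plans paired tests of change in daytime rest.

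**Conclusion.** The overlap is real and the plan does not address it. It does no harm where napping is stable. It favours a spurious link between more napping and worsening to the extent that napping changes between evaluations, most plausibly at week 6 against baseline. Under the stated assumptions, the false-positive rate is about 5% with stable habits, 7-11% if half of patients redraw their habit, and 12-32% in the two extreme cases. These figures illustrate the mechanism and do not predict this study's result.

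The point is confined to Table 3.4.1. The primary objective and the napping analysis by CTCAE grade are not affected. A reader might also infer that dropping item 9 would let the table show the effect of napping. It would not, because fatigued patients may nap more, and that reverse causation remains.

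**What to change.** In SAP 8.2.3 and Table 3.4.1, add the napping association on the sum of the 12 items without item 9. Do not rescale it by 13/12, and keep the same limit (a change of more than 4 raw points). Show it beside the 13-item result. Draw a conclusion about napping and FACIT fatigue only if it holds without item 9, and word it as an association. All other tables keep the 13-item score. State which rule governs unanswered items, so that Annex 1 and SAP section 7 agree.

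The cost is one derived variable and a few lines of SAP text. Protocol 7.3 lists only the FACIT score. If the database holds totals alone, item 9 must be entered from the questionnaires, which Protocol 7.4 keeps as source documents. The drawback is that the 12-item sum is not the validated total, which is why its use is limited to this table.

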## 4 HYPOTHESIS TESTING

The statistical significance value is set to p<0.05 The SPSS statistical package, V19.0 or later will be used.

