#### 8 STATISTICAL ANALYSIS AND METHODOLOGY

#### 8.1 STATISTICAL METHODS

The investigator will collect data from the enrolled patients in an electronic Case Report Form specially designed for this study.

The patient number we provide is a serial number devoid of any identifying value.

The information is stored in an Access database, which in turn is associated with a file, "WorkGroup", detailing the user code and permits of the investigator within the database. People not within this working group cannot access the database.

A Data Management Plan (DMP) will be developed and once approved by the person responsible for the study, the "Queries" will be programmed in the electronic case form so that when the investigator saves the data, it informs him/her of any doubts regarding the data.

All changes made by the investigators during the collection of data will be stored in a table specially designed for this purpose, indicating the user, date, modified field, the old value and the new value.

The fatigue-related quality of life of the patients and the quality of life of patients with palmar-plantar erythrodysaesthesia (hand-foot syndrome) will be studied using the mean, standard deviation and confidence intervals if they follow normal distribution, or the median, minimum, maximum and interquartile range if they do not follow Gaussian distribution. The Wilcoxon test will be used to analyse the inter-visit correlation for patients' quality of life.

The objective response rate according to RECIST version 1.1 will be studied using absolute and relative frequencies.

In order to study the impact of drug administration time, napping, temporary interruptions and dose reductions on fatigue and hand-foot syndrome control, independent samples will be compared using Pearson's chi-square test (or Fisher's exact test for 2x2 tables or likelihood ratio test for mxm tables, if necessary) in the case of qualitative variables and Student's t-test, one-way ANOVA test or non-parametric equivalents, such as the Mann-Whitney U test or Kruskal-Wallis H test in the case of quantitative variables.

The Kaplan-Meier survival estimate will be used to study both the PFS and TTF of patients. The log-rank test will be used to compare the survival distributions.

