## 8.2.3 Follow-up analysis

The evolution of the following aspects will be presented for each one of the follow-up visits of the patients at which the variables listed below are recorded:

- Presence of palmar-plantar erythrodysesthesia: the absolute and relative frequency of patients who as of month 3 of treatment develop palmar-plantar erythrodysesthesia of any grade will be provided. In the sub-population of patients with hand-foot syndrome, the frequency distribution will be presented according to the degree of severity of these AE, according to CTCAE (Common Terminology Criteria form Adverse Event) version 4:
  - o Grade 1
  - o Grade 2

#### o Grade 3

For each one of the evolution visits (month 6 and month 9), a study will be performed to ascertain whether significant changes have occurred in the presence and the grade of the HFS with regard to the previous visit, defined as (improved, maintained or worsened). The Pearson chi-squared test will be used for this purpose (or Fisher's exact test for 2x2 tables or likelihood ratio test for mxn tables, if necessary).

- Presence of fatigue: the absolute and relative frequency of patients with the presence of fatigue of any degree since the baseline visit will be provided. In the sub-population of patients with fatigue, the frequency distribution will be presented according to the degree of severity, according to CTCAE (Common Terminology Criteria form Adverse Event) version 4:
  - o Grade 1
  - o Grade 2
  - o Grade 3
  - o Grade 4

For each one of the evolution visits (month 3, month 6 and month 9), a study will be performed to ascertain whether significant changes have occurred in the grade of fatigue with regard to the previous visit, defined as (improved, maintained or worsened). Significant associations will be sought between the habits of daytime rest, physical aerobic exercise, medication taken, dose and treatment schedule changes, dose interruptions and the number of days of treatment interruption depending on the evolution of the presence and degree of fatigue in the last twelve weeks. The Pearson Chi-squared test will be used for this purpose (or Fisher's exact test for 2x2 tables or likelihood ratio test for mxn tables, if necessary).

- Patient diary data (weekly): the distribution of patient frequencies will be presented according to the following habits:
  - Napping
    - Every day
    - Weekend and/or holidays
    - Sporadically, between 2 or 6 days
    - Has not taken a nap any day

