#### • Physical exercise:

- I have not done any kind of physical exercise
- I have done at least 45 minutes of physical exercise 2-3 days a week
- I have done 45 min of physical exercise 4-5 days a week for at least 6 months
- I have done at least 45 minutes of physical exercise every day

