	.4	Association between daytime dose changes and evolution on the Facit_Fatigue (every six weeks)
	.5	Association between doses, daytime treatment regimen and evolution on the Facit_Fatigue (every six weeks)
	.6	Association between temporary daytime interruptions and evolution on the Facit_Fatigue (every six weeks)
.4	5	Treatment, dose changes and temporary interruptions
· ·	7	Efficacy analysis
	.1	Number of treatment cycles received
	.2	Best response rate achieved with first-line treatment
	.3	ORR, DOR
	.4	Time on treatment and time to best response
	.5	Time to Treatment Failure (TTF)
	.6	Progression-free survival (PFS)
	.7	Reason for termination of treatment and reason for death

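### For FACIT evolution tables the SAP's only small-count fallback is the asymptotic likelihood-ratio test, which under assumed margins often rejects 6-9% of the time at nominal 5%

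*SAP*

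**What the plan says.** For FACIT-Fatigue evolution, SAP 8.2.3 states: "The Pearson chi-squared test will be used for this purpose". The alternative in brackets is "Fisher's exact test for 2x2 tables or likelihood ratio test for mxn tables, if necessary". The paragraph on fatigue grade in the same section, the paragraph on hand-foot syndrome grade, SAP 8.1 ("likelihood ratio test for mxm tables, if necessary") and Protocol 7.7 carry the same fallback. None of them says when the fallback becomes necessary, or names an exact or Monte Carlo version for larger tables.

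Evolution is classed as improvement, maintenance or worsening. Maintenance applies "if the score on the quality of life scale does not vary by more than 4 points versus the previous evaluation".

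The explanatory variables also have several levels. Napping has four options, one being "Sporadically, between 2 or 6 days". Exercise has four, up to "I have done at least 45 minutes of physical exercise every day". Time of intake has four. Total days of interruption has three bands. Ten dose-and-regimen combinations are listed for description, and the table list in SAP 9 includes "Association between doses, daytime treatment regimen and evolution on the Facit_Fatigue (every six weeks".

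On the error rate, SAP section 4 says only: "The statistical significance value is set to p<0.05". SAP 5.1 plans 100 patients with 5% discontinuation, and SAP section 7 replaces no missing values.

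**The concern.** An analyst normally leaves the Pearson test because expected counts are too small for the chi-squared approximation. The likelihood-ratio statistic relies on the same approximation. At moderately small expected counts it often rejects too often, while Pearson stays near its nominal level. The SAP therefore moves from one large-sample test to another in the tables where large-sample theory is weakest, and often to the less accurate of the two. The exact test it does name is confined to 2x2 tables and cannot be reached when the outcome has three levels.

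At stake are the significant associations that the SAP says it will look for under secondary objectives 3 and 4 (exercise, napping, time of intake, interruptions, dose reductions). Because the condition for switching is undefined, the analyst can also choose between two tests that give different answers in sparse tables.

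**Working it through.** **The plan's own figure.** The 5% level is a set value. No attained error rate is stated for these tables, so there is nothing to reproduce.

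**Inputs from the documents.** Three outcome levels; three-, four- and possibly ten-level explanatory variables; 100 patients; 5% discontinuation, so 100 x (1 - 0.05) = 95.

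**Inputs assumed, because the documents give none.**
- Patients per table: 95, 70 or 50.
- FACIT splits (improved/maintained/worsened): from 33/33/33 through 25/50/25, 20/60/20 and 15/70/15 to 10/80/10.
- Row splits: eleven patterns with three, four, six or ten levels.

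**Are the tables sparse?** Take the common rule that no more than 20% of expected counts should be below 5.
- If the regimen table uses all ten listed regimens, it has 10 x 3 = 30 cells. At least 24 must have an expected count of 5 or more, which needs at least 24 x 5 = 120 patients. That exceeds the planned 100, whatever the split.
- A habit table has 4 x 3 = 12 cells. With four equal rows, FACIT 20/60/20 and n = 95, the eight cells outside maintenance each expect 95 x 0.25 x 0.20 = 4.75. So 8 of 12 cells are below 5.

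**Size of the two tests.** With E = row total x column total / n, Pearson is X² = Σ(O - E)²/E and the likelihood-ratio statistic is G = 2 Σ O ln(O/E). Each was compared with the 95% point of chi-squared on (r - 1)(c - 1) degrees of freedom, counting non-empty rows and columns. Tables were generated under independence, with 20,000 to 40,000 per scenario (Monte Carlo standard error about 0.1-0.15 percentage points). A scenario counted as sparse if most of its tables broke the 20% rule; 162 did.

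| 162 sparse scenarios | Likelihood ratio | Pearson |
|---|---|---|
| Range of size | 1.9-10.1% | 2.2-10.2% |
| Median size | 6.8% | 4.7% |

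The likelihood-ratio test rejected more often than Pearson in 78% of scenarios and was further from 5% in 75%. Its size lay between 6.5% and 9.5% in 59% of scenarios and below 5.5% in 25%.

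| Rows (%) | FACIT split (%) | n | Likelihood ratio | Pearson |
|---|---|---|---|---|
| 25/25/25/25 | 20/60/20 | 95 | 7.0% | 4.8% |
| 25/25/25/25 | 15/70/15 | 70 | 8.4% | 4.6% |
| 70/10/15/5 | 33/33/33 | 95 | 8.1% | 4.3% |
| Ten regimens* | 25/50/25 | 95 | 9.2% | 3.7% |
| 70/10/15/5 | 10/80/10 | 95 | 4.3% | 6.2% |
| 85/5/8/2 | 10/80/10 | 95 | 2.5% | 8.8% |
| Ten regimens* | 10/80/10 | 95 | 3.6% | 7.6% |

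*Assumed split 25/20/10/8/3/3/20/5/3/3.

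The first four rows show the common pattern. The last three show it reversed, with 80% in maintenance.

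**Size after the change.** A permutation test (3,000 replicates, 499 permutations each) in five sparse scenarios gave 4.3-5.5% with Pearson ordering and 4.1-5.8% with likelihood-ratio ordering. The Monte Carlo standard error is about 0.4 points, so both agree with 5%. The asymptotic likelihood-ratio test gave 2.5-8.4% in the same five scenarios.

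**The case against.** The strongest reply is that the inflation comes from the assumed splits. For another assumed ten-regimen split (30/20/8/12/2/3/17/5/1/2%), FACIT 20/50/30 gives 7.6-7.8% for the likelihood-ratio test at n = 95, 70 and 50. FACIT 15/70/15 gives 4.3-5.5%, and 10/80/10 gives 2.0-3.3% with Pearson at 7.8-8.8%. This stands. A reader might infer that these tables carry a fixed 7-9% false-positive rate, or that the fallback is always worse than Pearson; the documents supply no margins that would support either.

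Three narrower inferences also go too far.
- A 30-cell regimen table is a likely reading of SAP 9, but the SAP does not say that the table has ten rows.
- Fisher's test is unreachable for three-level FACIT evolution, but not everywhere. Severe fatigue (score below 30) against a yes/no exposure would be 2x2.
- Not every FACIT table is sparse. With a yes/no exposure present in 30%, FACIT 20/50/30 and n = 95, only about 1% of tables break the 20% rule. Pearson would be kept, with size 4.8%.

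On importance, the study is descriptive and these are secondary analyses. SAP 8.1 also allows t-tests, ANOVA and rank tests, so objective 4 does not rest on this test alone. Six FACIT association tables at six evaluations make 36 tests: 36 x 0.05 = 1.8 expected false positives at 5%, and 36 x 0.068 = 2.4 at the median found here. Unadjusted repetition therefore contributes more than the choice of test. That limits the consequence but does not defend the fallback, because the SAP explicitly looks for significant associations at p<0.05.

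**Conclusion.** The concern holds in a limited form. For FACIT evolution tables the only stated fallback is a likelihood-ratio test with no exact version. In sparse tables of this size it commonly rejects about 6-9% of the time at nominal 5%, and is usually further from 5% than the Pearson test it replaces. Over the margins examined its size runs from about 2% to 10%, and Pearson's range is similar. When most patients are maintained and one habit or regimen dominates, the likelihood-ratio test is conservative and Pearson liberal. The firm conclusion is that neither asymptotic test is reliable here and that the direction of error cannot be known in advance.

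This rests on assumed category splits, assumed numbers per evaluation and an asymptotic reading of the likelihood-ratio test. It concerns the error rate of each exploratory secondary test; multiplicity is a separate matter.

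**What to change.** In SAP 8.1, in the hand-foot syndrome, fatigue-grade and FACIT paragraphs of SAP 8.2.3, and in Protocol 7.7 for consistency, replace the likelihood-ratio fallback. For r x c tables, specify a Fisher-Freeman-Halton exact test or a Monte Carlo permutation p-value with at least 10,000 draws.

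Replace the undefined condition with a rule: either use this test for every such table, or use it when more than 20% of expected counts are below 5.

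If regimen categories are to be merged, fix the grouping before the data are examined. Keep dose level in any table meant to assess dose: merging by drug and schedule alone would remove dose from a table whose title names it.

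The cost is a change of wording and an exact or Monte Carlo option in the software. No new data are needed. Some borderline p-values will change, mostly to less favourable ones.
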